Measurement of mucus plugging with computer tomography before and following implementation of the AffloVest in adults with bronchiectasis – a feasibility study'

STUDY PROTOCOL – AFFLO Study

DATE 09/09/2019

CHIEF INVESTIGATOR

[name]

List Investigators

[name] [name] [name] [name]

Investigation Sites:

Royal Papworth Hospital NHS Foundation Trust, [name]

Protocol Identification Number: P02552

Date of Protocol: 09/09/2019

Protocol Version Number: 2

Trial Sponsor: Royal Papworth Hospital NHS Foundation Trust

Contents

TRIAL OVERVIEW

- 1. Trial Overview Primary Research Question Study Design Primary Outcome Secondary Outcome Rationale
- 2. Patient Recruitment Study Population Inclusion Criteria Exclusion Criteria Recruitment Strategy
- 3. Data Analysis Sample Size Statistical Analysis
- 4. Consent Process and Visit Schedule Visit 1 Follow-up Visit Informed Consent Procedure Table 2: Visit Schedule Table 3: Trial Specific Procedures *versus* Routine Procedures
- 5. Follow up Visits, Travel Expenses and Other Costs
- 6. Data Collection, Auditing and Retention of Documents Data Collection Form Completion Source Documentation Errors and Correcting Storage of Documents Retention of Documents Monitoring and Auditing Labelling of Source Documentation
- 7. Adverse and Serious Adverse Events Recording & Reporting
- 8. Amendments Amendment log
- 9. References

TRIAL OVERVIEW

1. Trial Overview

Principal Objective:

The principal objective is to test the feasibility of using computer tomography and the modified Brody score to measure the amount of mucus plugging within the lungs of adults with bronchiectasis at baseline and after six weeks treatment with the AffloVest. The study outcomes will facilitate the design of a future study to test treatment efficacy.

Study Design:

This is a feasibility study using computer tomography to measure the amount of mucus within the lungs of adults with bronchiectasis before and following implementation of the AffloVest. The aims of the study include assessing the feasibility of the study protocol and estimating the size and variability of the treatment effect with the AffloVest to facilitate the design of a future study to test treatment efficacy.

30 adult subjects (male and female) who have a known diagnosis of bronchiectasis and who attend the Cambridge Centre for Lung Infection (CCLI) at the Royal Papworth Hospital will be recruited.

Subjects will be recruited through convenience sampling and must demonstrate stability during a 2week period prior to enrolment. Stability is defined as no change in medical treatment.

Participants will be asked to use the AffloVest for 30 minutes twice daily (in addition to their standard airway clearance regimen where possible) for six weeks, with clinical review and tests performed at baseline, three and six weeks.

Tests to be performed at baseline, after three and six weeks of treatment with the AffloVest include: computer tomography (CT) at full inspiration and full expiration; spirometry (FEV1 and FVC); and the patient reported outcomes Visual Analogue Scale for ease of sputum clearance (VAS), St George's Respiratory Questionnaire (SGRQ) and Quality of Life–Bronchiectasis (QOL-B).

The CT images will be scored by two independent expert thoracic radiologists using the modified Brody Scoring System which is sensitive and reproducibe.¹² Both radiologists will be blinded to the time point of the CT scans being analysed and if there is disagreement in scores, an average will be taken.

We hypothesize that there will be a reduction in the amount of mucus plugging and an improvement in patient reported outcomes following implementation the AffloVest in adults with bronchiectasis.

Primary Outcome

The primary outcome of this study is to test the feasibility of using computer tomography and the modified Brody score to measure the amount of mucus plugging within the lungs of adults with bronchiectasis at baseline and after six weeks of treatment with the AffloVest. The study outcomes will facilitate the design of a future study to test treatment efficacy.

Secondary Outcome(s)

Secondary outcomes include the full modified Brody score, lung function, quality of life scores and a visual analogue score for ease of sputum expectoration measured at baseline, after 3 weeks of intervention and after 6 weeks of intervention. There will also be a sub-group analysis excluding patients that have a pulmonary exacerbation during the study.

Rationale

Bronchiectasis is a chronic inflammatory suppurative respiratory disease associated with poorer quality of life, increased admissions and increased mortality.^{1,2} The disease is characterised by a

AffloVest Study

clinical syndrome of cough, sputum production and recurrent respiratory infection, with radiological evidence of abnormal and permanent dilation of the bronchi.^{1,4} In the United Kingdom, incidence and prevalence rates are increasing with recent reports suggesting a current prevalence of 566 and 485 per 100000 patient years in women and men respectively.⁵

A major strategy in the management of patients with bronchiectasis is to optimise airway clearance and thereby reduce the inflammatory and infective burden in the lung. Several guidelines for airway clearance techniques have been created including the European Respiratory Society Guidelines for the management of adult bronchiectasis¹, and Guidelines for the physiotherapy management of the adult, medical, spontaneously breathing patient.⁵ However, no one technique has consistently been shown more effective than others and all the studies discussed in the guidelines were of poor quality. Furthermore, none of these guidelines evaluated High Frequency Chest Wall Oscillation (HFCWO).

First described in 1966 by Beck, HFCWO uses percussive forces, transmitted to the lungs to mobilise secretions to mimic effects or percussion and vibration without the need of a physiotherapist or caregiver.⁷ Traditional HFCWO machines use single waveforms delivered by large volumes of air at high amplitudes to rapidly inflate and deflate an air bladder. Conversely, the AffloVest uses mechanically generated pressure waveforms from 8 dynamic oscillating motors inside a vest. Current evidence for HFCWO has focused on cystic fibrosis (CF) and suggests that it is at least as effective as conventional physiotherapy in clearing secretions with improved patient adherance.⁷

Additionally, studies in asthma and chronic obstructive pulmonary disease (COPD) have shown that HFCWO may be beneficial for hospitalised patients through leading to reduced Borg dyspnoea scores, improved FEV1, increased sputum expectoration and reduced exacerbation frequency.^{8,9} Finally, HFCWO has been used by over 50,000 patient's suggesting it is safe and effective intervention in a number of airway diseases and is now recognised as standard of care in individuals with CF in North America.¹⁰

However, to date, there have been no studies of HFCWO in adult patients with bronchiectasis utilising CT to measure the amount of mucus within the lungs before and after implementation of this intervention. This study aims to assess the feasibility of the protocol and to estimate the size and variability of the treatment effect with the AffloVest to facilitate the design of a future study to test treatment efficacy in adults with bronchiectasis.

Schedule of Events

Day -21 to Day -1

• Informed consent and review of inclusion & exclusion criteria

Day 1 – Start of intervention

- CT scan; FEV1 and FVC; PROs (VAS for ease of sputum clearance, SGRQ & QOL-B).
- Participants will be shown how to use the AffloVest and will complete a skills checklist for home use.
- 3 weeks of AffloVest for 30 minutes twice a day (10 minutes each of percussion, vibrations and drainage at an intensity tolerable by each individual participant) in addition to their standard airway clearance regimen (where possible).

Day 21 – Midpoint of intervention

- CT scan; FEV1 and FVC; PROs (VAS for ease of sputum clearance, SGRQ & QOL-B); adherence check.
- 3 further weeks of AffloVest for 30 minutes twice a day (10 minutes each of percussion, vibrations and drainage at an intensity tolerable by each individual participant) in addition to their standard airway clearance regimen (where possible).

Day 42 – End of intervention

 CT scan; FEV1 and FVC; PROs (VAS for ease of sputum clearance, SGRQ & QOL-B), adherence check.

2. Patient Recruitment Criteria

Study Population

Participant number: n = 30

Population group: Adults (males and females) with bronchiectasis who attend the Cambridge Centre for Lung Infection, Royal Papworth Hospital NHS Foundation Trust

Time in study: A total of 63 days from enrolment

Inclusion

- Adult male and females ≥18 years
- Current diagnosis of bronchiectasis (see above definition)
- Productive of sputum on a daily basis
- Clinical stability over a 2-week period prior to enrolment (see above definition)

Exclusion

- Cystic fibrosis
- Severe obstructive airways disease (defined as FEV1 < 25%)
- Predominant lung disease is not bronchiectasis in the opinion of the investigator (e.g. asthma; COPD; pulmonary fibrosis)
- Bronchiectasis in only 1 lobe
- Currently treated non-tuberculous mycobacterial lung disease
- Acute congestive cardiac failure
- Contra-indication or unable to perform HRCT imaging, including pregnancy
- Contra-indication to using AffloVest including lung malignancy, recent rib fractures, radiological evidence of lung cavitation, and recent significant haemoptysis (in the opinion of the investigator)
- History of poor adherence to physiotherapy treatment
- Cognitive or memory problems affecting ability to follow instructions or give informed consent

Recruitment

The planned recruitment target is 30 participants. No strategies for promoting or boosting recruitment are deemed necessary, other than 'in-house' referral from respiratory physicians and physiotherapists working at the Cambridge Centre of Lung Infection, Royal Papworth Hospital.

Section 3. Sample Size and Data analysis

Sample Size:

N = 30.

There are currently no data on which to base an estimation of treatment effect following implementation of high frequency chest wall oscillation, nor what the minimal clinically significant change in CT parameters might be. Thus feasibility data are required to guide the design and power calculation of a future larger study to test treatment efficacy. In these circumstances, we have suggested a sample size of 30 patients, as we anticipate that this will allow sufficiently precise estimation of the size and variability of the treatment effect. Furthermore, if we encounter a drop out rate of 15%, a cohort size of 30 would generate 95% confidence intervals 2.2% and 27.8%.

Statistical Analysis:

To analyse the primary outcome, the CTs will be reviewed by two independent radiologists blinded to the time point for each scan and quantified using the "mucus component" of the modified Brody scoring system. If there is discrepancy on the score for an individual participant at one time point, the two scores will be averaged. After the modified Brody score for each patient is determined we will calculate summary statistics including group mean, standard deviation, standard error and confidence intervals at baseline and after 6 weeks of treatment. Other feasibility measures such as participant dropout rate will also be calculated.

Secondary outcome summary statistics including the full modified Brody score, FEV1, FVC, SGRQ, QOL-B, VAS score and adherence to treatment will be calculated at baseline, after 3 weeks of treatment and after 6 weeks of treatment. Any participants who suffer an exacerbation of their bronchiectasis during the trial will continue in the study and will be included in the analysis of the primary endpoint. However, an additional sub-group analysis will be undertaken excluding this population as a secondary outcome.

Finally, we will also carry out paired t-tests to assess change in CT, lung function and symptom parameters following implementation of the AffloVest. However, this is not the primary aim of this feasibility study and the study may be significantly underpowered to properly address this point. In any case, data generated by the study will inform the design of a larger trial to fully investigate efficacy. A p-value of 0.05 will be interpreted as statistically significant unless otherwise stated.

4. Consent Process and Visit Schedule

Visits

- Subjects will be approached about the study by the CCLI Research team, physiotherapy team or CCLI consultant team at an outpatient appointment, during a day case / inpatient visit or via postal invitation (if known to the service and deemed appropriate for the study). Once seen, and if deemed to be eligible for the study, they will be consented and enrolled.
- Each participant will be assigned a study number; the study numbers will be allocated sequentially starting at 10.
- Participants will then be arranged to undergo first visit testing with treatment and follow up according to the schedule below.
- Visits will be scheduled and performed according to table 1.
- Trial specific procedures *versus* routine procedures are detailed in table 2. The trial specific
 procedures will only be performed after written informed consent has been obtained.

Visit Number	Screening	Visit 1	Visit 2	Visit 3
Time interval of Visit	Day -21 to day -1	Day 1	Day 21	Day 42
Informed consent	X			
Review of inclusion & exclusion criteria	X	X		
Medical history and examination		X	X	X
Size for AffloVest	X			
Fit AffloVest, teach how to use it, check tolerance of settings		X		
AffloVest skills checklist of participant competency		X	X	X
AffloVest adherence tracking			X	X
Spirometry (FEV ₁ and FVC)		X	X	X
Pregnancy test if appropriate (urine dipstick)		X	X	X
Patient reported outcomes (VAS, SGRQ & QOL-B)		X	X	X
CT scan		X	X	X

Table 1Visit Schedule

Informed Consent Procedure

- Subjects will receive written and verbal information about the trial.
- Written informed consent will be obtained by a member of the trial team using the Patient Information and Consent Form (PICF). Consent will only be obtained after a suitable time has elapsed during which the subject has had ample time to read the information sheet, consider

the trial and ask any questions. The Investigator or appropriate delegate will explain to each subject the nature of the study, its purpose, the procedures involved, the expected duration, the potential risks and benefits involved and any discomfort it may entail. The signed PICF will be scanned and uploaded electronically onto the hospital's secure electronic medical records.

- The ultimate responsibility for obtaining written informed consent lies with the Investigator but this responsibility may be delegated to a suitably trained and experienced person.
- Prior to the subject's participation in the study, the written informed consent form will be signed and personally dated by the subject and by the clinician who conducted the informed consent discussion. Each box at the end of each statement on the consent form will be signed by the subject.
- Each subject will be informed that participation in the study is voluntary and that he/she may withdraw from the study at any time and that withdrawal of consent will not affect his/her subsequent medical treatment.
- A copy of the informed consent document will be given to the participant. One copy will be filed in the participant's hospital case notes and uploaded on the password locked hospital electronic medical records.
- The Principle Investigator or research delegate will ensure that the subject does not have any trial specific procedures prior to giving informed consent.
- If a participant withdraws their consent a line will be drawn diagonally through the consent form and labelled 'consent withdrawn' and signed and dated by a member of staff and uploaded into the electronic medical record.

Follow up Visits:

The follow up visits will be in accordance with the visit schedule outlined in table 1. Participants will be seen at each visit by one of the principal investigators.

If the participants choose to consent to it, the study organisers may contact participants after the study has completed to request feedback regarding the longer-term experience of using the AffloVest.

Travel Expenses:

Reasonable travel expenses will be reimbursed for each study visit.

Study Costs:

- 30 HFCWO AffloVests (provided by International Biophysics)
- 90 inspiratory and expiratory CT scans (3 per participant) with reporting by two independent
- radiologists £437 each (Total = £39,330)
- 90 FEV₁ measurements (3 per participant) £45 per time point per patient (Total = £4,050)
- Pregnancy test covered by Royal Papworth Hospital where applicable
- Physiotherapist time (£177 per patient) £5,310
- CI time £1,962
- R&D overheads (20%) £10,130
- Total £60,782
- Total costs (Travel and Study Costs): £65,28230

5.

Data Collection, Auditing and Retention of Documents

Data Collection Form Completion

 The Investigator will ensure the accuracy, completeness, legibility and timeliness of the data recorded and in all required reports to e.g. the Sponsor, Funder, R&D, REC.

Source Documentation

6.

The investigator/clinical research nurses will maintain electronic clinical case notes on the hospital's secure electronic medical record system. This will include all demographic and clinical information. A copy of the patient information and consent form will also be uploaded electronically in the patient's case notes (see above section on consent). All information will be traceable to and consistent with the participant's hospital electronic case notes.

Errors and Corrections

 Any change or correction will be dated, initialled, and explained (if necessary) and will not obscure the original entry (i.e. an audit trail will be maintained).

Storage of Documents

 Electronically uploaded forms and electronic clinical case notes will be stored securely on the hospital's password locked electronic medical records.

Retention of Documents

 All study specific documentation will be stored for 12 months after the last patient has completed their last visit.

Monitoring and Audit

- Upon request of the monitor, auditor, Sponsor, R&D, REC, MHRA or other regulatory authority, the Investigator will make available for direct access all requested study-related records.
- The project data will monitored by an appointed member of the R&D department at the Royal Papworth Hospital NHS Foundation Trust.

Section 7. Adverse and Serious Adverse Events

The definition of an adverse event is: 'Any untoward medical occurrence in a patient which does not necessarily have a causal relationship with this treatment'. This includes 'any unfavourable and unintended sign (including an abnormal laboratory finding), symptom or disease temporally associated with the study drug'. This may include, for example, a cold or an accident.

The definition of a serious adverse event is one that fulfils at least one of the following criteria:

- Is fatal- results in death
- Is life threatening
- Requires inpatient hospitalisation or prolongation of existing hospitalisation
- Results in persistent or significant disability/incapacity

OR

Is a congenital anomaly/birth defect

The definition of a suspected unexpected serious adverse reaction (SUSAR) is a serious adverse event that is thought to be possibly or definitely related to the study drug.

Recording and Reporting

- Studies have shown HFCWO to be safe. There are however risks involved with HFCWO and FEV₁ including haemoptysis, rib fractures, tenderness, bronchospasm, breathlessness and fainting. These occur rarely and supervision and guidance throughout testing procedures will also minimise the chance of risks occurring. There is equal chance of these risks occurring during patient's normal medical care and airway clearance treatments.
- Additional ionising radiation exposure via 3 low dose HRCT's over the 28-day period will occur. The estimated radiation dose per scan is 3.6mSv. The total research protocol dose is therefore 11mSv, which is equivalent to that received, on average in the UK, from natural sources of background radiation in approximately 5 years. For adults in the general population, this dose is estimated to correspond to a cancer risk of around 1 in 2,500. This can be compared with the natural lifetime risk of cancer in the UK of about 1 in 2 and it should be noted that the latency period for radiation induced cancer is about 5 years for leukaemia and decades for solid tumours.
- All research staff in contact with participants will be responsible for noting adverse events that are reported by the patient and making them known to the Principal Investigator. All AE's will be documented in the participant's electronic clinical case notes, as per usual standard of care.
- At each visit or study assessment, adverse events that have occurred since the previous visit will be elicited from the patient. The event will be detailed in the participant's electronic clinical case notes, as source document verification, including the start date (if known) and end date.
- The action taken regarding the study procedure will be documented.
- Any treatment/medication given for the event, including the dates the treatment/medication was commenced and the date it was stopped/changed, if applicable, will be documented.
- Documenting of adverse events will be the responsibility of the Principle Investigator, Co-Investigator and Clinical Research Nurse/Assistant
- Events, which are ongoing at the final study visit, will be followed up as clinically indicated.
- All serious adverse events (SAEs) and suspected unexpected serious adverse reactions (SUSARS) will be documented as above.
- SUSARS will be reported to the Sponsor within 48 hours of the Chief / Principle Investigator/Clinical Research Nurse being aware.
- All Unexpected SAEs and SUSARs will be reported to the hospital R&D department and may be require analysis through the hospital incident reporting system.
- Expected SAEs will be reported to the Main REC in the annual REC report; the REC who
 performed the locality assessment does not need to be informed.
- All completed SAE forms will be uploaded to the participant's electronic medical record.

8. Amendments

Substantial amendments will be submitted to the Health Research Authority and Research Ethics Committee for review and approval.

9. References

- 4. Koser U and Hill A. What's new in the management of adult bronchiectasis? *F1000Research.* 2017;6:527. DOI:10.12688/f1000research.10613.1.

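### The 2-week stability requirement ends at enrolment, 1 to 21 days before the baseline CT, so as worded it does not secure stability in the 2 weeks before that scan (probably small effect, cheap fix)

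*Protocol*

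**What the plan says.** The Study Design text in section 1 says that subjects "must demonstrate stability during a 2week period prior to enrolment. Stability is defined as no change in medical treatment". The inclusion list in section 2 repeats the requirement with the same anchor: "Clinical stability over a 2-week period prior to enrolment (see above definition").

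Section 4 (Visits) says when enrolment happens. Patients are seen and, "if deemed to be eligible for the study, they will be consented and enrolled". The next step comes after that: "Participants will then be arranged to undergo first visit testing with treatment and follow up according to the schedule below".

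The Schedule of Events places "Informed consent and review of inclusion & exclusion criteria" in the window Day -21 to Day -1, and the first CT on Day 1. Section 2 also gives "Time in study: A total of 63 days from enrolment".

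Table 1 marks "Review of inclusion & exclusion criteria" at both Screening and Visit 1, and "Medical history and examination" at Visits 1, 2 and 3.

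On exacerbations, section 3 keeps participants who have one during the trial in the primary analysis and adds a secondary sub-group analysis without them.

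**The concern.** A stability criterion in a before-after study serves to make the baseline measurement representative of the patient's usual state. Here the criterion is tied to an administrative event that can precede the baseline scan by up to three weeks. A participant could enrol on Day -15, have a treatment change on Day -5, and still meet the criterion as written when scanned on Day 1.

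This matters because there is one group, and the baseline scan is the only comparator. The study's stated aims include estimating the size and variability of the treatment effect for a later trial. A disturbance before Day 1 that has resolved by Day 42 enters the change score. It can act either way: an exacerbation that raises the baseline mucus score makes the fall look larger, and a treatment change that lowers it for a time makes the fall look smaller. In both cases it adds to the variability of change.

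**Working it through.** **1. Where enrolment falls.** The only stated figure that bears on this is the 63 days in the study. The longest screening gap plus the intervention period is 21 + 42 = 63 days. The figure is reproduced if enrolment is at consent and there is no Day 0, which agrees with section 4.

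**2. Coverage of the 14 days before the CT.** With enrolment k days before Day 1 (k = 1 to 21), the days covered are max(0, 14 − k).

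| Gap k (days) | Days covered, of 14 |
|---|---|
| 1 | 13 |
| 7 | 7 |
| 13 | 1 |
| 14 to 21 | 0 |

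Coverage is zero for 8 of the 21 possible gaps. If enrolment were spread evenly over the window (an assumption), mean coverage would be 91/21 = 4.3 of 14 days. If a Day 0 were counted, gaps would be 2 to 22 days, with zero coverage for 9 of 21 and a mean of 3.7 days.

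**3. Possible size.** The protocol gives no event rate, no effect of an event on the score and no distribution of enrolment days. The following are assumptions:
- events (treatment change or exacerbation): 1 to 3 per patient-year;
- enrolment spread evenly over the 21 days;
- effect d of an event on the baseline score: 0.5 to 1 SD, in units of the SD of the change score;
- full resolution by Day 42;
- all events in one direction (relaxed in step 4).

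Re-anchoring reaches only events in the uncovered part of the last 14 days, that is min(k, 14) days, with mean 203/21 = 9.67 days. The share addressed is f = mean over k of 1 − exp(−rate × min(k, 14)/365).

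| | Rate 1 per year | Rate 3 per year |
|---|---|---|
| f | 0.026 | 0.076 |
| Participants, of 30 | 0.8 | 2.3 |
| Shift f × d, d = 0.5 | 0.013 SD | 0.038 SD |
| Shift f × d, d = 1 | 0.026 SD | 0.076 SD |

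**4. Scale.** Section 3 considers 15% dropout: 30 × 0.85 = 25.5, taken as 26 pairs.
- The 95% CI half-width for the mean change is t(0.975, 25)/√26 = 2.060/5.099 = 0.404 SD. The largest shift is 0.076/0.404 = 0.19 of it.
- The SD of change becomes √(1 + f(1 − f)d²), which is 1.003 to 1.034. With a noncentral t distribution at n = 26 and two-sided 0.05, the paired t-test rejects in 5.05% to 6.5% of studies with no treatment effect, instead of 5%.
- If directions split evenly, the mean shift is 0 and the SD of change is √(1 + f d²), which is 1.003 to 1.037: an increase of 0.3% to 3.7%.

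**5. Comparison with the treatment period.** At the same rates, the share with an event in the 42 treatment days is 1 − exp(−rate × 42/365), which is 0.109 and 0.292, or 11% to 29%.

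**The case against.** The strongest case against the point has four parts.

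*Nothing is contradicted.* Sections 1 and 2 state the same criterion with the same anchor, and tying stability to enrolment with a short screening window is a coherent choice. This stands. A reader might infer an internal contradiction, but there is none: the criterion is clear and consistent, and its anchor is simply weak for the purpose.

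*Visit 1 already acts as the eligibility gate.* Table 1 repeats the criteria review on Day 1 with a medical history, and section 4 makes Table 1 govern the visits. Spirometry and the pregnancy test, which bear on exclusions, are also first done there. A careful investigator may well recheck stability. This mitigates the gap in practice, and the document does not show that unstable patients would be scanned. It does not remove the gap, because the criterion under review still ends at enrolment. The Schedule of Events lists the review only in the screening window, but that is a summary; adding it under Day 1 would change nothing.

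*The sub-group analysis deals with it.* This stands only in part. Counting study time from enrolment suggests that an exacerbation in the gap is one during the study, so the participant would be left out of that analysis. But it is secondary, the primary analysis keeps these participants, and a treatment change without an exacerbation is not covered.

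*The size is assumed and small.* This stands. A lasting treatment change could affect both scans and need not enter the change score as modelled. The primary outcome is feasibility, and the paired t-tests are expressly not the main aim.

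**Conclusion.** The point holds as a low-priority improvement. What rests on the text alone is that the stability window ends at consent, that the baseline CT follows 1 to 21 days later, and that nothing requires stability up to the scan.

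The size rests wholly on the assumptions listed in the working. Under them the avoidable shift in mean change is 0.013 to 0.076 SD, in either direction. Its upper end needs the highest rate, the largest effect, full resolution and every event acting the same way.

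Two stronger readings are not supported. One is that the gap materially biases the estimated effect in the vest's favour: the direction is open, and even the largest value is under a fifth of the study's own imprecision. The other is to charge every event in the gap to this wording: events more than 14 days before Day 1 lie outside any 2-week window, so moving the anchor would not reach them. Exacerbations during treatment, kept in the primary analysis by design, are a larger source of the same noise and are not part of this point.

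**What to change.** In the Study Design text of section 1 and the inclusion list of section 2, let the existing 2-week criterion run up to Visit 1 (Day 1) instead of enrolment, with the definition of stability unchanged. State that it is confirmed before the baseline CT, at the Visit 1 eligibility review already in Table 1.

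All 14 days before the scan are then covered whatever the screening gap. The cost is a short wording amendment, with no new visit or test and no change to the sample size. The downside is that a few Day 1 visits would be rescheduled or a few consented participants would become screen failures.

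### The aims and the sample-size rationale promise a precise *treatment effect*, but one uncontrolled cohort can give only within-participant change, and the only precision figure given is for dropout

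*Protocol*

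**What the plan says.** Section 1, Study Design, lists among the aims "estimating the size and variability of the treatment effect with the AffloVest to facilitate the design of a future study to test treatment efficacy". The Rationale repeats that the study is meant "to estimate the size and variability of the treatment effect with the AffloVest to facilitate the design of a future study".

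Section 3, Sample Size, starts from a lack of prior information: "There are currently no data on which to base an estimation of treatment effect following implementation of high frequency chest wall oscillation", and no minimal clinically significant change in CT parameters is known either. It concludes: "Thus feasibility data are required to guide the design and power calculation of a future larger study to test treatment efficacy". It then proposes 30 patients because "we anticipate that this will allow sufficiently precise estimation of the size and variability of the treatment effect". The only figure that follows is this: "if we encounter a drop out rate of 15%, a cohort size of 30 would generate 95% confidence intervals 2.2% and 27.8" (a percentage).

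Section 3, Statistical Analysis, describes the primary summaries of the mucus component as including "group mean, standard deviation, standard error and confidence intervals at baseline and after 6 weeks of treatment". Change is assessed by paired t-tests. The Protocol says that these are not its main purpose and may be badly underpowered.

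On design, the Schedule of Events and the visit table show one cohort with CT on Days 1, 21 and 42 and the vest started on Day 1. Study Costs budgets 30 vests for 30 participants. No control group or untreated observation period with repeat CT is described.

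**The concern.** A treatment effect is a contrast between what happens with the vest and what would have happened without it. This design observes only the first. A change in mucus score between Day 1 and Day 42 combines any effect of the vest with natural variation in mucus load, with exacerbations, and with changes in the participants' usual airway clearance, which the Protocol asks them to keep up only where they can. Participants who have an exacerbation "will continue in the study and will be included in the analysis of the primary endpoint". A larger sample would make the change more precise but would not separate these parts.

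The label matters because of the Protocol's own reasoning. It says that no effect data exist, and that this study is needed to guide a later power calculation. If the observed change is reported as the treatment effect with no statement that it is uncontrolled, the later trial's designers could take it for a between-group difference.

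Separately, the claim of sufficient precision is attached to the effect, but no figure for any CT score or change supports it.

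**Working it through.** **1. The Protocol's own interval.** Inputs from Section 3, Sample Size: n = 30, dropout p = 0.15. The simple normal-approximation interval is p ± 1.96 × √(p(1 − p)/n).

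- √(0.15 × 0.85/30) = √0.00425 = 0.0652
- 1.96 × 0.0652 = 0.128
- 0.15 ± 0.128 = 2.2% to 27.8%

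This matches the stated figure. The arithmetic is reproduced, and the interval concerns dropout alone. It carries no information on the precision of a CT score.

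**2. What the design can estimate.** Set the passages side by side:

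| Feature | Protocol | Consequence |
|---|---|---|
| Groups | One cohort, all given the vest | No between-group contrast |
| CT before treatment | Day 1 only | No estimate of change without the vest |
| CT on treatment | Days 21 and 42 | Paired change from baseline is estimable |
| Stated aim | Size and variability of the treatment effect | Not identified by the above |

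**3. Precision of the paired change.** The Protocol gives no SD, so results are in units of the SD of change. Pairs available: 30 with no dropout; 30 × 0.85 = 25.5 at the Protocol's 15%, shown as 25 and 26.

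Mean change: 95% CI half-width = t(0.975, n − 1)/√n.

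SD of change: the 95% CI multiplies the estimate by √((n − 1)/χ²), using the upper and lower 2.5% points of chi-square on n − 1 degrees of freedom.

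| Pairs | Half-width of mean change (in SDs of change) | CI for SD (× estimate) |
|---|---|---|
| 30 | 2.045/√30 = 0.37 | √(29/45.72) = 0.80 to √(29/16.05) = 1.34 |
| 26 | 2.060/√26 = 0.40 | √(25/40.65) = 0.78 to √(25/13.12) = 1.38 |
| 25 | 2.064/√25 = 0.41 | √(24/39.36) = 0.78 to √(24/12.40) = 1.39 |

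A later sample size that uses the SD of change scales with its square. With 25 pairs, that factor runs from 24/39.36 = 0.61 to 24/12.40 = 1.94.

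**4. How far the SD interval can be trusted.** It relies on roughly normal changes. Simulating 25 pairs, the nominal 95% interval covered the true SD about 95% of the time for normal data, about 82% for a moderately skewed distribution (gamma, shape 2) and a little over 70% for an exponential one. The distribution of the mucus score change is not given, so the SD widths should be quoted with that condition.

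**The case against.** The best defence is that this is openly a feasibility study. The title and Study Design describe a before-and-after comparison, the primary outcome is whether CT and the modified Brody score can be used to measure mucus plugging, and efficacy is left to a larger trial. The Statistical Analysis section speaks of change after the vest is introduced and concedes low power. There are also real safeguards: two weeks of clinical stability before enrolment, radiologists blinded to time point, and an additional analysis excluding participants with exacerbations. And with no prior data, precision could be stated only in SD units, which follow from n alone.

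Much of this stands, and it limits the severity. But low power is a caveat about precision and does not answer a missing control. The safeguards reduce some sources of bias and supply no comparator. Precision in SD units is easily stated, and it is what the word *sufficiently* needs behind it.

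A reader might infer more than the documents support:

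- **That 30 is the wrong number, or that a control arm is required.** Neither follows. A feasibility sample need not come from a power calculation, and a single cohort can serve the primary outcome.
- **That the later trial will be powered on this change.** The Protocol does not say so. It says only that the data will guide the design and power calculation.
- **That the loss of power in the later trial can be put in figures.** That needs the share of the change not due to the vest. The documents give none, and any value would be invented.
- **That failing to name the SD of change is a fault in itself.** The list of primary summaries is open, the paired t-tests yield the SD, and a statistical analysis plan may name it.

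**Conclusion.** The point holds as a minor one. The aims and the sample-size rationale claim a quantity that the design cannot identify. The Protocol nowhere says that the change it will observe is uncontrolled, and its claim of precision rests on no relevant figure.

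What the study can deliver is the mean within-participant change to within about ±0.37 to ±0.41 SD of change, and the SD of change to within roughly 20% below and 34% to 39% above its estimate. The ranges span 30 to 25 complete pairs. The half-width for the mean is the usual t interval. The SD limits assume roughly normal changes and are too narrow if changes are skewed. Whether these widths are good enough is for the sponsor to judge once they are stated. No conclusion about feasibility is affected.

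**What to change.** 1. In Study Design, Rationale and Sample Size, replace *treatment effect*, where it names what this study will estimate, with *within-participant change from baseline to 6 weeks*.
2. In Sample Size, replace the claim of sufficient precision with the expected widths. For the mean change, give a 95% CI half-width of about 0.37 SD of change with 30 pairs and about 0.41 with 25. For the SD of change, give about 0.80 to 1.34 times the estimate with 30 pairs and 0.78 to 1.39 with 25, noting that these hold only for roughly normal changes and are too narrow under skew. Keep the dropout interval, labelled as such.
3. In Statistical Analysis, report the mean and SD of the paired change in the mucus component, with the CI of the mean, beside the planned paired t-test. These are descriptive estimates and do not become the primary outcome.
4. Add one sentence saying that the change is uncontrolled and so does not estimate the vest-versus-control difference for the later power calculation.

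The sample size stays at 30, and no visit, scan or control arm is added. The costs are a less favourable statement of what the study delivers and possibly a protocol amendment. Under Section 8, an amendment judged substantial goes to the Health Research Authority and the ethics committee.
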